### 6.6.1. Missing Efficacy Endpoints – Proteinuria and eGFR Slope

#### 6.6.1.1. Primary Analysis

For the primary analysis of primary endpoint of proteinuria and key secondary efficacy endpoints of eGFR slopes, missing central laboratory data will be imputed using the multiple imputation (MI) procedure ([Ouyang 2017](#), [Rubin 1987](#)). Under the missing at random (MAR) assumption, a Bayesian multivariate normal model for the data will be fitted using a Markov Chain Monte Carlo (MCMC) approach. Quasi-independent samples will be drawn from the posterior distributions for the parameters of the multivariate normal distribution for each arm. A non-informative prior will be used. The MCMC approach allows all missing observations to be imputed, whether a patient has monotone or non-monotone pattern of missingness. Monotone missing pattern is when a data point is missing for an individual patient then all subsequent data points are missing for that patient, whereas a non-monotone missing pattern implies data points are missing in intermediate visits for a patient. The seed number for the random generator will be defined and documented before study unblinding.

Following the approach described in [Ouyang \(Ouyang 2017\)](#), the following imputation procedures will be implemented:

1. Intermittent missing values before a discontinuation event (ie, discontinuation of randomized therapy or early permanent dropout): the MAR assumption is reasonable for intermittent missing values before a discontinuation event since the values of the endpoint before and after the intermittent missing value are known. Imputation of intermittent missing data will be accomplished using the MCMC option in SAS PROC MI (SAS, 2008) by treatment group to impute intermittent missing data without a monotone missing pattern, prior to performing imputations of values following the discontinuation event.
2. Missing data following a discontinuation event (ie, discontinuation of randomized therapy or early permanent dropout): impute the post discontinuation missing data by treatment group under the assumption of MAR using the regression option from the monotone statement of SAS PROC MI. Baseline and post-baseline scheduled visits will be used in the regression option to impute the missing values.
3. Repeat Steps 1 and 2 to generate 30 multiply imputed datasets.
4. The mixed model (ie, the analytic model) analysis described for the endpoint will be performed on each set of the newly "complete" data (observed data plus imputed values).
5. Using Rubin's approach ([Rubin 1987](#)), the estimated treatment effects are combined across imputations. This will be accomplished using SAS PROC MIANALYZE.

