### 12.2. Sample Size Justification

The hypothesis to be tested relating to the change in proteinuria at Week 36 post-randomization is as follows:

$$H_0: \Delta = 0 \text{ versus } H_1: \Delta \neq 0$$

where  $\Delta$  is the true difference between sparsentan and irbesartan in the log change from baseline in proteinuria at Week 36. Based on data from the Leicester University Hospital Registry of IgA nephropathy patients (Leicester IgAN Patient Registry) in over 350 patients with IgAN (who were not treated with steroid therapy) provided by [name], together with proteinuria data published by Inker et al (Inker 2016), the standard deviation of the log change from baseline in proteinuria at Week 36 is estimated to be 0.92. A total of 280 randomized patients will, therefore, provide at least 90% power to test that the true relative treatment effect on proteinuria, sparsentan versus irbesartan, is at least 30%. Based on the data published in Inker, this degree of treatment effect is predicted to reflect a treatment effect on clinical outcomes (doubling of serum creatinine, ESRD, or death) with a hazard ratio of 0.36 and a 95% confidence interval (CI) of (0.22, 0.61). In addition, [name] patient registry database indicates that a 30% treatment effect on proteinuria at the patient level predicts a difference in the slope of eGFR decline that translates to an estimated difference in eGFR at 104 weeks (approximately 2 years) of 6.64 mL/min/1.73 m^2, with a 95% CI of (0.83, 12.44).

Approximately 380 patients will be required to detect an underlying treatment effect in the rate of change in eGFR over 110 weeks following the initiation of randomized therapy (eGFR total slope at 2 years) of 2.9 mL/min/1.73 m^2 per year with 90% power. In addition, approximately 380 patients provide 80% power to detect a smaller treatment effect on eGFR total slope at 2 years of 2.55 mL/min/1.73 m^2 per year. Consequently, approximately 380 patients provide more than 90% power to detect an underlying treatment effect in the rate of change in eGFR over 104 weeks following the initial acute effect of randomized therapy (eGFR chronic slope at 2 years) of 3.15 mL/min/1.73 m^2 per year. With this sample size, the observed annualized treatment difference to yield a p-value of <0.02 is 1.8 mL/min/1.73 m^2 per year. These sample size and power calculations follow the method described by Dupont (Dupont 1998), with

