### 4.3. Sample Size Considerations

#### 4.3.1. Sample Size Justifications

The hypothesis to be tested relating to the change in proteinuria at Week 36 post randomization is

$$H_0: \Delta = 0 \text{ versus } H_1: \Delta \neq 0$$

where  $\Delta$  is the true difference between sparsentan and irbesartan in the log change from baseline in proteinuria at Week 36. Based on data from the Leicester University Hospital Registry of IgA nephropathy patients (Leicester IgAN Patient Registry) in over 350 IgAN patients (who were not treated with steroid therapy) provided by [name], together with proteinuria data published by Inker et al (Inker 2016), the standard deviation (SD) of the log change from baseline in proteinuria at Week 36 is estimated to be 0.92. A total of 280 randomized patients will therefore provide at least 90% power to test that the true relative treatment effect on proteinuria, sparsentan versus irbesartan, is at least 30%. Based on the data published in Inker et al (Inker 2016), this degree of treatment effect is predicted to reflect a treatment effect on clinical outcomes (doubling of serum creatinine, ESRD, or death) with a hazard ratio of 0.36 and a 95% confidence interval (CI) of (0.22, 0.61). In addition, [name] patient registry database indicates that a 30% treatment effect on proteinuria at the patient level predicts a difference in the slope of eGFR decline that translates to an estimated difference in eGFR at 104 weeks (approximately 2 years) of 6.64 mL/min/1.73 m^2, with a 95% CI of (0.83, 12.44).

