### 6.5.4. Visit Windows

A visit window method will be applied to determine analysis visits across the study for efficacy and safety endpoints based on laboratory results, including eGFR and quantitative urinalysis (including UP/C). If a patient has multiple assessments (including unscheduled visits) within a visit window, the value closest to the target day for that visit will be selected for analysis. If more than 1 assessment is equidistant to the target day, then latest value will be selected. For efficacy analysis visits on or prior to Week 110, only assessments while the patient is on randomized treatment should be included (see [Section 8.1](#) for definition of on treatment).

The visit windows for the double-blind period shown in [Table 1](#) are defined for endpoints based on laboratory results. Visit windows for the OLE will be defined in a separate SAP.

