## **8.6. Analysis of the Key Secondary Efficacy Endpoints**

### **8.6.1. Rate of Change in eGFR Following Acute Effect of Randomized Therapy**

The rate of change in eGFR over 52 weeks and 104 weeks following acute effect will each be analyzed via a mixed model random coefficients analysis. The dependent variable will be eGFR measured over 52 weeks (Week 6 to Week 58) or over 104 weeks (Week 6 to Week 110). The model will include the following fixed effects:

- Treatment group (2 levels: sparsentan, irbesartan)
- Baseline eGFR
- Time (ie, analysis visit in weeks)
- Treatment group by time interaction
- Randomization stratification variable (4 levels based on Screening eGFR and urine protein excretion)

In addition, the model will also include a random intercept and random slope for each patient.

Under the assumption of MAR, missing data will be imputed using the MI procedure (Ouyang 2017, Rubin 1987). Specific imputation procedures are provided in [Section 6.6.1.1](#).

An unstructured covariance matrix will be assumed; if convergence issues arise, a first order autoregressive structure will be used.

The treatment effect will be the contrast between sparsentan and irbesartan marginal slope estimates. The associated slope estimates, difference in slopes, 95% CI, and 2-sided p-value will be extracted from the model. Slope and the difference in slopes will be annualized for ease of presentation and interpretation.

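### The eGFR imputation conditions on eGFR visits alone; adding the randomization stratum and baseline UP/C would protect the slope comparison if discontinuation depends on proteinuria differently by arm

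*SAP*

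**What the plan says.** SAP 6.6.1.1 sets out two imputation steps for the main analyses of UP/C and of the eGFR slopes. Intermittent gaps are filled by MCMC, "by treatment group to impute intermittent missing data without a monotone missing pattern". For values after a discontinuation event the instruction is to "impute the post discontinuation missing data by treatment group under the assumption of MAR", using monotone regression. The predictors are given in one sentence: "Baseline and post-baseline scheduled visits will be used in the regression option to impute the missing values". No stratum appears in either step and, for eGFR, no proteinuria variable. The section does not say that they are excluded.

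The models fitted to the completed data are richer. SAP 8.5.1, 8.6.1 and 8.6.2 each list as a fixed effect the "Randomization stratification variable (4 levels based on Screening eGFR and urine protein excretion"). In the two slope models it is a main effect only; the one time interaction listed is treatment by time.

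The load on the imputation follows from SAP 6.5.4: for efficacy visits through Week 110, "only assessments while the patient is on randomized treatment should be included". SAP 8.1 ends the on-treatment period 3 days after the last dose. An eGFR value collected later, as protocol 6.3.2 encourages, is set aside and replaced by an imputed one.

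On the link between proteinuria and eGFR, protocol 12.2 states that "a 30% treatment effect on proteinuria at the patient level predicts a difference in the slope of eGFR decline", and SAP 4.3.1 repeats its size: an "estimated difference in eGFR at 104 weeks (approximately 2 years) of 6.64 mL/min/1.73" m², with a 95% CI of 0.83 to 12.44.

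**The concern.** Missing at random is an assumption given the variables in the imputation model. Here that means eGFR history within arm. Screening proteinuria is known for every patient, was judged important enough to stratify on, and is plausibly related to the rate of eGFR loss. Baseline eGFR carries the eGFR half of the stratum but not the 1.75 g/day half.

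Suppose patients above 1.75 g/day decline faster and stop treatment more often than their eGFR history explains. Those who stop are then imputed from others with similar eGFR histories but, on average, slower decline, and the arm's slope comes out too flat. If this happens more in one arm, the difference between slopes shifts. These imputations feed the confirmatory slope tests, so the stake is the size and error rate of those tests.

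**Working it through.** **1. The plan's own slope figures.** The documents state no figure for the imputation, but the power statement gives a yardstick. Inputs from SAP 4.3.1: 380 patients (190 per arm), one-sided α 0.02, residual error 5.8, 90% power at 2.9 per year.

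- Implied SE = 2.9 / (2.054 + 1.282) = 0.869. The critical difference is 2.054 × 0.869 = 1.79; the SAP says 1.8.
- Direct formula: SE = 5.8 × √(2/190) / 0.676 = 0.881, where 0.676 years is the SD of the Week 6 to Week 110 visit times. This gives power of 89.2% at 2.9, 80.0% at 2.55 and 93.6% at 3.15. The spread of visits that the plan used is not stated; with all visits from Day 1, power at 2.9 would be 94.4%.

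The plan's figures are reproduced closely enough to use 0.87.

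**2. Does eGFR history stand in for the stratum?** Take a patient seen from Day 1 to Week 36: visits at 0, 2, 4, 6, 12, 24 and 36 weeks. The squared deviations from the mean of 12 weeks sum to 1064, and √1064 = 32.6 weeks = 0.627 years. The SE of that patient's own slope is 5.8 / 0.627 ≈ 9.2 per year. With an assumed between-patient slope SD of 3, reliability is 9 / (9 + 85) ≈ 10%; with SD 5 it is 25 / (25 + 85) ≈ 23%. Early history says little about slope.

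**3. A ceiling by hand.** Assume half the patients are in the high stratum, with 35% (high) and 15% (low) discontinuing.

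- Overall discontinuation is 25%. High stratum among those who stop: 0.175 / 0.25 = 70%; among those who stay: 0.325 / 0.75 = 43.3%.
- If follow-up were entirely missing and history uninformative, the arm's slope would be too flat by 0.25 × (0.700 − 0.433) × gap = 0.067 × gap. That is 0.13, 0.27 and 0.47 for slope gaps of 2, 4 and 7 per year.

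On-treatment visits and eGFR history should bring the bias below this.

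**4. Simulation.** The setup was 150,000 patients per arm at the protocol's visits, residual SD 5.8, a true difference of 2.9 and a within-stratum slope SD of 3 (assumed). Imputation was sequential regression within arm on eGFR visits. Conditional means were imputed, because imputation noise averages out of a bias. The table shows the bias per year in the slope difference (sparsentan minus irbesartan) without the stratum.

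| Gap between strata | 35% vs 15% on irbesartan only | 35% vs 15% on sparsentan only | Same pattern in both arms |
|---|---|---|---|
| 2 | −0.08 | +0.08 | within 0.01 (each arm too flat by 0.08) |
| 4 | −0.17 | +0.15 | within 0.01 (each arm too flat by 0.16) |
| 7 | −0.25 | +0.24 | within 0.01 (each arm too flat by 0.25) |

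- Discontinuation unrelated to stratum, or driven only by observed eGFR: bias within 0.02 for every gap.
- Stratum added to the imputation: bias within about 0.02 in every scenario.
- A harsher case, 45% vs 15% on irbesartan and 10% on sparsentan: −0.14, −0.26 and −0.41.
- Repeating the one-arm cases with stops spread evenly from Week 12 to Week 110 again gave 0.08 to 0.25. Timing matters. In a related case (slopes −6 and −3; 30% and 10% stopping in one arm, 15% and 10% in the other) the bias was 0.15 with early stops, 0.08 with even spread and 0.04 with late stops.

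**5. What it would do.** Power at 2.9 is Φ((2.9 + b)/0.869 − 2.054). It is 90% at b = 0, 88% at −0.08, 86% at −0.17 and 84% at −0.25. One-sided type I error is 1 − Φ(2.054 − b/0.869). It is 0.020 at b = 0, 0.025 at +0.08, 0.032 at +0.17 and 0.038 at +0.24.

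**6. A caution on the yardstick.** The planning SE behaves as if each patient gave one observation. Under the simulation's own components at a gap of 4, with complete data, SE = √[(2/190) × (9 + 4 + 6.7)] ≈ 0.46. Here 4 = (4/2)² is the between-stratum variance and 6.7 = 5.8² / (11 × 0.676²). If the actual SE is smaller than 0.87, the same bias weighs more.

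**The case against.** The strongest objection is that the harm needs three conditions, and the documents assert none of them. The stratum must predict slope beyond eGFR history, discontinuation must depend on the stratum given that history, and that dependence must differ between arms. Protocol 6.3.2 lists reasons for stopping but gives no rate and no link to proteinuria. This stands, and it is why the point is conditional.

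A reader might infer from protocol 12.2 that the protocol itself says the screening stratum predicts slope. It does not. The sentence concerns a treatment effect on proteinuria and supports the stratum as a predictor only indirectly.

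A reader might also see an error of mismatch between imputation and analysis models. That too goes too far. The slope models carry the stratum without a time interaction. Fitted to observed data without imputation, they gave nearly the same bias as imputation without the stratum (0.083 against 0.084, and 0.130 against 0.135, in two scenarios). The change enriches the imputation beyond the analysis model; it does not repair an inconsistency. The same result means that the planned no-imputation analysis of on-treatment data would not reveal the problem.

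The SAP has other safeguards. The treatment-policy analysis in 8.6.3 uses observed values after discontinuation, but it targets a different estimand. The tipping-point analysis in 6.6.1.2 worsens imputed sparsentan values by far more than the amounts above, so it covers a bias toward sparsentan. It leaves irbesartan unadjusted and does not address the opposite case. Both are sensitivity analyses and leave the main estimate as it is.

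Finally, the SAP is silent on strata rather than explicit, and it follows a cited published approach not available here. If strata were intended, a sentence saying so settles that part.

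**Conclusion.** The point holds as a possible bias that is cheap to prevent. As written, eGFR after discontinuation is imputed within arm from eGFR alone. If higher-proteinuria patients decline faster and stop more often given their eGFR history, the imputed values can be too flat; if the pattern differs between arms, the slope difference can be biased toward or against sparsentan.

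For 35% versus 15% discontinuation in one arm only, the bias is about 0.08 to 0.25 mL/min/1.73 m² per year, or 9% to 29% of the implied SE of 0.87. This rests on assumed stratum gaps of 2 to 7 per year, equal-sized strata, a slope SD of 3 and the assumed timing of stops. None of these is in the documents. The bias is about zero if discontinuation is unrelated to the stratum, and it cancels in the difference if the pattern is the same in both arms.

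It would be tempting to conclude that imputed eGFR is necessarily too flat or that the slope tests are biased. The omission alone does not imply either. No harm is shown for UP/C, where baseline log UP/C already carries most of the proteinuria stratum.

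**What to change.** In SAP 6.6.1.1, state the full PROC MI variable list for each endpoint. For eGFR, add to steps 1 and 2, within arm, the four-level stratum recorded in the IRT (as indicator variables) and baseline log UP/C. For UP/C, add the stratum for consistency only. If the strata were already meant to be included, say so. Settle this before unblinding, as the section already requires for the random seed.

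The cost is a sentence or two in the SAP and, for eGFR, four more predictors per arm (three indicators and one covariate). No new data are needed, and the estimand and analysis models do not change.

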### **12.7.2.3. Type I Error Control for Efficacy Endpoints – Double-blind Period**

At the time of the primary analysis of change from baseline in UP/C, approximately 222 patients are projected to have eGFR data up to 58 weeks. If the analysis of UP/C at Week 36 yields a two-sided p-value <0.05, analysis of the key secondary endpoints will proceed.

[figure not shown]
For non-US countries, at the time of primary analysis of proteinuria, the key secondary endpoint of rate of eGFR rate of change over 6 to 58 weeks will be formally assessed at the 1% two-sided alpha level. Type I error control for the additional key secondary endpoints at confirmatory analysis will be governed at this time by a gate-keeper on the 6- to 58-week eGFR rate of change at the 1% level. The subsequent key secondary (confirmatory) endpoint analyses of eGFR rate of change over 6 to 110 weeks and eGFR rate of change over 110 weeks following initiation of randomized therapy will be tested sequentially and be assessed at the 4% two-sided alpha level if the 6- to 58-week eGFR rate of change analysis fails to achieve  $p < 0.01$ ; otherwise, subsequent key secondary (confirmatory) endpoint analyses will be assessed at the 5% two-sided alpha level.

For the US, at the time of primary analysis of proteinuria, the endpoint of rate of change over 58 weeks will not be formally tested. The key secondary (confirmatory) endpoint analyses of eGFR rate of change over 110 weeks following initiation of randomized therapy and eGFR rate of change over 6 to 110 weeks will be tested sequentially and assessed at the 5% two-sided alpha level.

The 2 confirmatory endpoints are intended to support regulatory submissions in the US (rate of change in eGFR over 110 weeks following initiation of randomized therapy) and non-US countries (6- to 110- week eGFR rate of change); hence, no further multiplicity adjustment is necessary. The Type I error control framework for the primary proteinuria and key secondary endpoints for US and non-US countries are displayed in [Figure 5](#). At the time of the final analysis, if all the key secondary endpoints achieve statistical significance, the other secondary endpoints will be statistically tested at the available alpha. For all other supportive efficacy endpoints, nominal p-values will be presented without Type I error control.

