### 8.4.1. Procedure for Non-US Countries

Analysis of key secondary endpoints will proceed as follows:

1. At the time of the primary analysis of proteinuria, the key secondary endpoint of rate of eGFR rate of change over 6 to 58 weeks will be tested at a significance level of  $\alpha = 0.01$ .
2. If significant at Step 1,  $\alpha = 0.01$  will be recycled and the next key secondary efficacy endpoint, eGFR rate of change over 6 to 110 weeks, will be tested at a significance level of  $\alpha = 0.05$  at the final analysis.
3. Otherwise (not significant at Step 1), eGFR rate of change over 6 to 110 weeks will be tested at a significance level of  $\alpha = 0.04$  at the final analysis.
4. The next key secondary efficacy endpoint of eGFR rate of change over 110 weeks from initiation of randomized therapy will be tested at a significance level of  $\alpha = 0.05$  (if significant at Step 1 and 2) or  $\alpha = 0.04$  (if significant at Step 3).

If at Step 2 or 3, the statistical comparison of treatment group is not statistically significant at the specified significance level, then the remaining comparisons will be considered descriptive and exploratory.

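### With only 30 imputations, the UP/C and key secondary slope p-values carry avoidable seed-to-seed noise near their significance limits

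*SAP*

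**What the plan says.** SAP 6.6.1.1 makes multiple imputation the primary analysis for the UP/C endpoint and the "key secondary efficacy endpoints of eGFR slopes, missing central laboratory data will be imputed using the multiple imputation (MI) procedure". Step 3 sets the number: "Repeat Steps 1 and 2 to generate 30 multiply imputed datasets". Each completed data set is analysed with the mixed model, and by Rubin's rules "the estimated treatment effects are combined across imputations". On the seed it says: "The seed number for the random generator will be defined and documented before study unblinding".

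What counts as missing is wide. For efficacy visits up to Week 110, SAP 6.5.4 says that "only assessments while the patient is on randomized treatment should be included", and SAP 8.1 ends the on-treatment period 3 days after the last dose. Later values are not used in the formal test, and step 2 of SAP 6.6.1.1 imputes them.

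The pooled p-values meet fixed limits. Outside the US, Protocol 12.7.2.3 has the "eGFR rate of change over 6 to 58 weeks will be formally assessed at the 1% two-sided alpha level" at the time of the primary analysis. The two-year slopes are then to "be assessed at the 4% two-sided alpha level if the 6- to 58-week eGFR rate of change analysis fails to achieve" p<0.01, and otherwise at 5%. SAP 8.4.1 repeats this: after a significant 58-week result, "eGFR rate of change over 6 to 110 weeks, will be tested at a significance level of" 0.05, and otherwise 0.04. The US sequence (SAP 8.4.2) uses 0.05 and does not formally test the 58-week slope. UP/C is tested at 0.05.

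The documents give no reason for 30, no Monte Carlo error criterion and no rule for a p-value close to a limit.

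**The concern.** A pooled estimate from a finite number of imputations varies from seed to seed, and so does its estimated standard error. With 30 data sets this variation may be large enough, close to 0.01, 0.04 or 0.05, for one pre-set seed to give a pass and another a fail on the same patient data. What is at stake is the formal result on UP/C or a slope and, outside the US, whether the two-year slopes are tested at 5% or 4%. The other secondary endpoints also depend on the key secondary results (SAP 8.4.3). The tipping-point analysis (SAP 6.6.1.2) is defined by where significance is lost, so it inherits the same noise.

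**Working it through.** **1. The plan's own figures.** SAP 4.3.1 gives a critical observed slope difference of 1.8 per year at one-sided 0.02 (4% two-sided). SE = 1.8/2.054 = 0.876. Power = Φ(δ/SE − 2.054), which gives 89.5% at 2.9, 80.4% at 2.55 and 93.8% at 3.15, against the stated 90%, 80% and more than 90%. For UP/C, 2(1.960 + 1.282)²(0.92)²/(ln 0.7)² = 139.8 per arm, or 280 in total, as stated. These figures reproduce.

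**2. Share of variance due to imputation (λ).** The documents do not give it, so it is an assumption. A random-coefficients calculation on the double-blind visit schedule used residual SD 5.8 (SAP 4.3.1) with assumed slope SD 4-8 per year, intercept SD 10 and stopping spread evenly over visits. It gives λ of about 0.05 at 10% discontinuation, 0.16-0.19 at 30% and 0.21-0.26 at 40%. I use 7%, 18% and 24%. For Week 36 UP/C and the 58-week slope, λ was not derived separately.

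**3. Seed-to-seed SD of z with M imputations.**

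SD(z)² = λ/M + [z × 0.5 × λ × √(2/(M−1))]²

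The first term is noise in the pooled estimate, the second noise in its SE. For M = 30, λ = 0.18 and z = 2.054: 0.18/30 = 0.0060; (2.054 × 0.09 × 0.2626)² = 0.0024; SD = √0.0084 = 0.091.

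| λ | 5% limit (z 1.960) | 4% limit (z 2.054) | 1% limit (z 2.576) |
|---|---|---|---|
| 7% | 0.052 | 0.052 | 0.054 |
| 18% | 0.090 | 0.091 | 0.099 |
| 24% | 0.109 | 0.110 | 0.121 |

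**4. On the p scale (SD 0.09).** Call the p-value with unlimited imputations the long-run p. A long-run p of 0.040 is z = 2.054; ±1.96 × 0.09 gives z from 1.877 to 2.230, or p from 0.060 down to 0.026. A long-run p of 0.030 is z = 2.170; it misses the 4% limit with probability Φ(−(2.170 − 2.054)/0.09) = Φ(−1.29), about 10%.

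**5. Second route.** Simulating the full Rubin-pooled p-value (t reference, complete-data df assumed 370, M = 30) with the long-run p placed at the limit gives these central 95% ranges over seeds:

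| Fraction of missing information | Limit 0.05 | Limit 0.04 | Limit 0.01 |
|---|---|---|---|
| 0.1 | 0.038-0.068 | 0.030-0.055 | 0.0072-0.0153 |
| 0.2 | 0.033-0.079 | 0.026-0.065 | 0.0059-0.0194 |
| 0.3 | 0.029-0.090 | 0.023-0.075 | 0.0049-0.0238 |

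These are slightly wider and shifted upward, because this route also carries the (1 + 1/M) factor and the t reference.

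**6. How often it would matter.** Over all possible results, the chance that two seeds disagree is about (2/√π) × SD(z) × φ(zα − δ/SE). At λ = 0.18 and the 4% limit:
- True difference 2.9 per year: 1.128 × 0.091 × φ(−1.255) = 1.128 × 0.091 × 0.182 = 1.9%.
- True difference 1.8 per year: 1.128 × 0.091 × 0.399 = 4.1%.

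The simulation, over missing-information fractions 0.1-0.3 and limits of 4-5%, gives 1.2-2.9% and 2.9-5.9%.

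**7. Validity.** With one pre-set seed, simulated type I error is 0.049 at 5% and 0.0094 at 1%. Going from 30 to 1,000 imputations changes power at 2.9 per year by at most about 0.5 point.

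**8. Imputations needed for SD(z) below 0.02.** M ≈ (λ + z²λ²/2)/0.0004. This gives about 200-220 at λ = 7%, 600-720 at 18% and 880-1,080 at 24%, depending on the limit. With M = 1,000, SD(z) is 0.016 at λ = 18%, and a long-run p of 0.040 ranges over 0.037-0.043. At λ = 24% and the 1% limit it is 0.021, just above the target.

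**The case against.** The best defence is that nothing is invalid. The seed is documented before unblinding, so nobody can choose it, and the test keeps its level. That stands. A reader might infer that 30 imputations inflate type I error; the documents do not support this. Inflation would need seed selection (best of 10 seeds: 0.061-0.074 at 5%), and the plan already rules that out. Fixing the seed does not remove the noise, however. It only fixes which draw is used.

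Second, the plan has seed-free checks: SAP 8.5.2 and 8.6.3 repeat the models on observed data without imputation. These could expose a seed-driven result, but they are sensitivity analyses and do not settle the formal test.

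Third, a reader might infer that a miss at 1% blocks the later tests. It does not. Under SAP 8.4.1 the two-year chronic slope is still tested, at 0.04 instead of 0.05, and the 1% test belongs to the non-US sequence only.

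Fourth, the size rests on an assumed λ and the effect is rare away from a limit. Both are true and hold the severity down. Even at a missing-information fraction of 0.05, though, the range at the 5% limit is 0.042-0.062.

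**Conclusion.** The point holds as a minor one. Thirty imputations leave a seed-to-seed SD of z of about 0.05-0.12 near the limits for imputation shares of 7-24%. That is enough for the seed to decide a borderline result, and it can be avoided. Unconditionally it is uncommon: two seeds would disagree in about 1-3% of trials at the design effect and 3-6% at a true difference of 1.8 per year. It is a matter of arbitrariness and reproducibility, not of error control or power. The existence of the noise follows from the plan. Its size depends on assumed stopping rates and slope variability, which the documents do not give.

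**What to change.** Before unblinding, replace 30 in step 3 of SAP 6.6.1.1 by a larger number, for example 1,000, for the primary, key secondary and tipping-point analyses. Add that the number will be raised if needed until the Monte Carlo SE of the pooled z-statistic is below 0.02, and that this SE will be reported. The criterion should govern rather than the round number: fewer than 1,000 are enough at small imputation shares, and 1,000 falls just short at a 24% share and the 1% limit. Keep the pre-set seed.

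The cost is computing time and more mixed-model fits, repeated over the tipping-point grid, with more occasions to meet the convergence fallbacks. SAP 8.5.1 and 8.6 give no rule for a single imputed data set that fails to converge, so one sentence on that should be added. No patients or alpha are spent, and the estimand and model do not change.
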